## 5:1 Investigational product

The trial drug will be L-alanyl-L-glutamine 20% (Dipeptiven®) concentrated solution for intravenous infusion, which will be delivered during 12 h intravenously.

## 5:2 Package and labelling

The trial drug as well as placebo will be manufactured by Fresenius-Kabi and will be provided in 100 ml glass bottles. Labelling will be performed by Apoteksbolaget. As treatment period will be variable among patients, the drug will be delivered to each centre marked A or B. Local Pharmacy will then according to randomisation deliver daily supply to the unit for each patient labelled with the unique 6-digit number given to the patient. Amont of drug administered and time interval of administration will be registered and reported daily.

## 5:3 Blinding and code breaking

Ala-gln 20% or 0.9% NaCl will have same appearance. The subject number will be noted on the label and on the bottle. Each subject number will consist of 6 digits. The investigator allocates the treatment by assigning subject number in a strict consecutive order. A list of the treatments geiven to the individual patients according to their 6-digit number will be kept at the local Pharmacy until interim analysis and until end of the study.

#### 5:4 Case Report Form as source data

The Case Report Form will be filled in daily and reported electronically to the study coordinator. Paper copies will be signed and filed at each study centre. The information on the Case Study Form will be considered as primary data.

## 6. Selection and withdrawal of subjects

All patients that receive nutrition in the ICU are eligible for inclusion into the study and may be included until discharge form the unit.

### 6:1 Screening

Screening will be performed when it is decided to prescribe full nutrition to the patient, usually during the initial 2 days of ICU-stay before the trial starts. During the screening following tasks will be performed.

- a) Detailed patient/relative information by the investigator and handout of the written patient/relative information
- b) List of inclusion/exclusion criteria will be checked
- c) Subject's demographic data will be controlled

Recording of APACHE II score at admission (during first 24 h of stay)

#### 6:2 Inclusion criteria

Subjects will be enrolled in the trial when they meet the following criteria:

- a) admission to the ICU
- b) decision to give the patient full nutrition
- c) APACHE II score >10 at admission
- d) age 18-85 years

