#### 1. Summary

This is a prospective double-blinded placebo-controlled block randomised study in intensive care patients comparing intravenous glutamine supplementation (0.285 g/kg body weight/24 h) to placebo. Inclusion criteria are patients treated for more than 3 days. Primary endpoint is a reduction in SOFA-score on day 7 of treatments. Secondary endpoints are: ICU-mortality, 6-months mortality, length of ICU stay, organ failure free days as well as reduction in SOFA-score on day 10 of treatment. Nutrition will be standardised so that not less than 80% of the target which is basasl energy expenditure according to Harris & Benedict is given daily. Enteral nutrition is preferred, but a combination of enteral and parenteral nutrition is recommended to achieve the nutritional target. Diagnosis and APACHE II score are registered at submission. After that the study drug, nutrition and SOFA-score will be registered on a daily basis. For statistical power calculations, a possible effect upon mortality as well as a limited effect of a short treatment period are considered. For statistical comparison non-parametric rank order statistics will be used. To detect a 0.75-point difference in the reduction of SOFA-score on day 7 of treatment, a total of 1,000 patients will be needed. Patients from 20-25 centre in the Nordic countries will be included in the study over a period of 18 months.

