## 4:1 Primary objective

The primary objective is to compare the change in SOFA-score (Appendix 8:2) on day 7 of ICU stay as compared to the day starting nutritional treatment and glutamine supplementation. Only patients who have received glutamine for not less than 3 days will be considered.

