#### 6:5 Randomisation

Subjects will be randomised to treatment only if they satisfy all inclusion criteria. The trial will include 500 subjects in each treatment group. Block randomisation means that the subjects will be assigned randomly to active or placebo treatment with equal size of the two treatment groups at each investigational centre. A computer program using the method of random allocation within fixed blocks will generate a randomisation list. It will provided for a defined number of subjects and a defined number of reserve subjects at each investigational centre. The randomisation list will be securely locked away during the trial by the responsible statistician until clean file has been declared.

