#### **10. Statistics**

The study is designed with one primary endpoint as the primary objective and several secondary endpoints as secondary objective. The statistical power calculation to determine the sample size is performed for the primary endpoint. Parametric and non-parametric statistics will be used depending on whether the parameters are normally distributed or not. As 3 days of treatment is an inclusion criteria all calculation will be made on included as well as randomised patients (intention to treat)

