#### 10:4 Multi-centre

The major centres in the Scandinavian countries do not have more than approximately 100 patients that stay for more than 5 days in the ICU, therefor a multi-centre design of the study is necessary. It is also desirable that the study can be concluded within 18 months. It is also desirable that each centre participating contribute with not less than 25 patients. It is therefor

natural that this protocol is a multi-centre study in the Scandinavian countries. The plan is to recruit 500 patients in 10 centres in Sweden and 500 patients in 10 centres in Denmark, Finland and Norway.

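### Three days of treatment is called an inclusion criterion but can be known only after randomisation; section 6:2 has no expected-stay criterion, so short-stay patients enter and are then dropped or dilute the comparison

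*Protocol*

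**What the plan says.** The Protocol describes the 3-day condition in several ways.

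- **Summary (section 1):** "Inclusion criteria are patients treated for more than 3 days".
- **Section 10:** "As 3 days of treatment is an inclusion criteria all calculation will be made on included as well as randomised patients", with the randomised patients labelled as intention to treat.
- **Section 6:2:** after "Subjects will be enrolled in the trial when they meet the following criteria" come four items: ICU admission, a decision for full nutrition, APACHE II above 10, and age 18 to 85. Neither treatment duration nor expected stay appears.
- **Section 6:5:** "Subjects will be randomised to treatment only if they satisfy all inclusion criteria".
- **Section 6:** "All patients that receive nutrition in the ICU are eligible for inclusion into the study and may be included until discharge form the unit".
- **Section 4:1:** "Only patients who have received glutamine for not less than 3 days will be considered".
- **Section 10:6:** a randomised patient counts as *included* once treatment starts. Patients with fewer than 3 treatment periods are classed as withdrawals, and 3 periods on consecutive days are needed for evaluation. The intention-to-treat set holds everyone randomised, including those with less than 3 days of treatment.
- **Section 5:** 1,000 patients are to receive glutamine or placebo on 3 or more consecutive days.

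**The concern.** Study treatment follows randomisation, so treatment received cannot be a condition for randomisation. Read literally, the Summary, section 10 and section 6:5 cannot all be followed. Section 10:6 adds a different meaning of *included*, namely that treatment has started.

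The practical consequence matters more than the label. The trial wants to evaluate patients treated for at least 3 days (4:1, 5, 10:6), but the entry list does not ask whether a patient is likely to stay that long, and entry remains open until discharge. Some short-stay patients will therefore be randomised, and the plan handles them in two ways, each with a cost:

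- **Dropping them** selects patients on death, discharge or discontinuation after randomisation. Treatment may affect all three, so the two arms of the remaining set are no longer protected by randomisation.
- **Keeping them** preserves the randomised comparison but includes patients with little exposure, which pulls the estimated difference towards zero.

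Section 10:3 states no explicit allowance for either.

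**Working it through.** **Inputs from the Protocol.** Difference to detect 0.75 SOFA points, power 80%, about 500 per arm (10:3); 500 per group (6:5).

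**Inputs not given, hence assumed.** SD, significance level and sidedness, and the share q of patients who leave before 3 treatment days. I take two-sided 0.05 and q from 10% to 30%. I also assume no effect in short-stayers, no replacement, and that 0.75 is the effect in patients treated for at least 3 days.

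**Step 1: calibrate to the plan's figure.** Without an SD, 500 per arm cannot be reproduced forwards. Solving backwards:

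SD = 0.75 / [(1.960 + 0.842) × √(2/500)] = 0.75 / (2.802 × 0.06325) = 4.23

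With SD 4.233 the standard error of the difference is 4.233 × 0.06325 = 0.2677. Power is Φ(0.75/0.2677 − 1.96) = Φ(0.84) = 0.80, as intended. This is a calibration and does not confirm the sample size. Other significance levels imply other SDs: 4.77 at one-sided 0.05 and 3.85 at two-sided 0.025.

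**Step 2: keep short-stayers (intention to treat).** The effect becomes 0.75 × (1 − q), and power = Φ(0.75(1 − q)/0.2677 − 1.96).

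**Step 3: discard short-stayers.** The number per arm becomes 500 × (1 − q), and power = Φ(0.75 / [4.233 × √(2/(500(1 − q)))] − 1.96).

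| q | Diluted effect | Power, kept | Evaluable per arm | Power, discarded |
|---|---|---|---|---|
| 0% | 0.750 | 80% | 500 | 80% |
| 10% | 0.675 | 71% | 450 | 76% |
| 20% | 0.600 | 61% | 400 | 71% |
| 30% | 0.525 | 50% | 350 | 65% |

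To hold 80% power, the number randomised per arm would be 618, 782 or 1,021 if they are kept, and 556, 625 or 715 if they are discarded.

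**Step 4: sensitivity to the significance level.** Once 80% at 500 per arm is accepted, the SD cancels and the power with short-stayers kept is Φ((1 − q)(z_α + 0.842) − z_α). At q = 20% this is Φ(0.8 × 2.486 − 1.645) = 63% at one-sided 0.05, and Φ(0.8 × 3.083 − 2.241) = 59% at two-sided 0.025. The assumed level changes the picture little; q and the zero-effect assumption drive it.

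**Step 5: the other reading of the 1,000.** If section 5 means 1,000 patients who each complete 3 days, the 3-day set has 500 per arm and keeps 80%. That set is still selected after randomisation, and the intention-to-treat comparison is still diluted.

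**The case against.** The strongest reply is that the entry procedure works as written. Section 6:1 has staff check a list at screening, section 6:2 is that list, and section 10 uses the 3-day rule to separate analysis sets. On that view the defect is one of wording. This is largely right about how the trial would run: a reader might infer that randomisation is impossible under this protocol, and the documents do not support that. It does not explain why the Summary and section 10 name an inclusion criterion that 6:2 lacks, and it confirms that the rule acts after randomisation.

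Second, entry does select partly for longer stay. A decision for full nutrition is required, screening usually falls in the first 2 ICU days, APACHE II must exceed 10, and exclusion b in 6:3 leaves room for the physician's judgement. A reader might infer that the entry rule makes no such selection, or that most patients would leave early. The documents give no early-leaver rate and support neither. Nor does 10:4, with its "patients that stay for more than 5 days in the ICU", define a target population; it explains why many centres are needed.

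Third, a reader might take the power figures above as the trial's actual power. They are not:

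- Section 10:3 says that a limited effect over a short treatment period was considered. If that covers short exposure, 0.75 is already diluted and step 2 counts the dilution twice.
- Section 6:5 provides reserve subjects at each centre, so short-stayers may be replaced.
- Section 5 can be read as 1,000 completers.
- No effect in short-stayers is the pessimistic end.

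Fourth, a reader might infer that excluding expected short-stayers costs nothing because they are not evaluated anyway. That is wrong twice: 10:6 analyses them under intention to treat, and imperfect prediction will turn away some patients who would have completed 3 days.

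**Conclusion.** The point stands as a mislabelled criterion combined with a gap between who is admitted and who is to be evaluated. The Summary and section 10 present treatment received as an inclusion criterion, although it is unknowable at randomisation, absent from 6:2, and at odds with the meaning of *included* in 10:6. Entry selects only partly for longer stay and stays open until discharge ("may be included until discharge form the unit"), so some short-stay patients will be randomised and then either filtered out or carried with little exposure.

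The documents do not fix the size of the loss. Under the assumptions set out with the calculation, it is about 9, 19 or 30 percentage points of intention-to-treat power at 10%, 20% or 30% early leavers, and about 4, 9 or 15 points if they are discarded. If the 1,000 are completers, the 3-day set loses no power, but selection after randomisation and intention-to-treat dilution remain.

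An expected-stay criterion alone does not settle the matter, because the filter in 4:1 and 10:6 would still remove those whose stay was wrongly predicted.

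**What to change.** 1. Add to 6:2 a fifth criterion, judged and recorded by the attending physician before randomisation: the patient is expected to need at least 3 further days of ICU treatment. Apply it equally to patients included late under section 6.
2. Delete the statements in sections 1 and 10 that treatment received is an inclusion criterion, and give *included* one meaning throughout.
3. Make all randomised patients the primary comparison and the 3-day set supportive, changing 4:1 and 10:6 to match. Section 8:1 already supplies an endpoint value for patients discharged or dead before day 7. Reconcile this with 10:7, which treats drop-outs before day 7 as withdrawals.
4. State in 10:3 and section 5 whether the 1,000 counts patients randomised or patients completing 3 days, whether reserve subjects replace early leavers, and whether 0.75 already allows for short exposure.
5. Reconcile the duration wording: the Summary and section 8 require more than 3 days, while sections 4, 4:1, 5 and 7 accept exactly 3.

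The cost is one screening line and an amendment. The eligible pool becomes smaller and the prediction will be imperfect, so some patients who would have been evaluable are lost and some short-stayers still enter. As an illustration only, halving early leavers from 20% to 10% would raise intention-to-treat power from about 61% to 71%, roughly 10 of the 19 points lost. The documents give no basis for how accurate the prediction would be.

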#### 6:3 Exclusion criteria

Subjects will be excluded for anyone for the following reasons:

a) readmission to the ICU after a previous ICU-stay in which the patient has been included into the study. Dismissal and readmission may be regarded as one treatment period if the absence of treatment is not more than 24 hours.

b) subjects with any condition which in the opinion of the attending physician makes the subject unsuitable for inclusion.

#### 6:4 Withdrawal of subjects

Patient's participation may be terminated at any time at the discretion of the investigator or at the patint's/relative's request. Should this happen the following information will be recorded: a) subject's/relative's comments or complains

b) reason for termination

#### 6:5 Randomisation

Subjects will be randomised to treatment only if they satisfy all inclusion criteria. The trial will include 500 subjects in each treatment group. Block randomisation means that the subjects will be assigned randomly to active or placebo treatment with equal size of the two treatment groups at each investigational centre. A computer program using the method of random allocation within fixed blocks will generate a randomisation list. It will provided for a defined number of subjects and a defined number of reserve subjects at each investigational centre. The randomisation list will be securely locked away during the trial by the responsible statistician until clean file has been declared.

#### 7. Treatment

Patients will receive a daily support of undiluted L-alanyl-L-glutamine (Dipeptiven®) containing glutamine 0.13 g/ml or placebo-treatment (NaCl) as a 12 h intravenous infusion during at least 3 consecutive days. In the trial the patients will receive intravenous administration of glutamine 0.285 g/kg/body weight or placebo treatment during 12 h intravenous infusion each day. The dosage of glutamine in relation to body weight will not continue above 90 kg, which is the upper limit.. The volume to be infused will depend upon the subject's body weight and calculating from the formula 0.285 g/kg body weight/12 h corresponding to a infusion rate of 0.024 g/kg body weight/h. The infusion may be done in a

central venous line or in a peripheral line. As Dipeptiven contains 20 g alanyl-glutamine per 100 mL, corresponding to 13 g of glutamine per 100 mL, the infusion rate will be 0.183 mL/kg body weight/h (Appendix 8.4). The treatment will continue as long as the patient stays in the ICU.

In parallel nutritional support of the patient will be standardised. The recommended routine is that the energy content should comprise no less than 80% of basal energy expenditure according to Harris & Benedict (Appendix 8.3). Preferably the enteral route should be used. If enteral nutrition is not sufficient to correspond to 80% of the energy expenditure, parenteral nutrition should be given complementary. It is recommended that a combination of enteral and parenteral nutrition is planned initially and that follow-ups during each 24-hour period are done to guaranty that every patient is given not less than 80% of the targeted nutrition. As routines will differ somewhat in between units this recommendation is given and nutrition will be recorded on a daily basis in terms of the energy content and nitrogen administered. Dipeptiven®/Glavamin® may not be used as concomitant medication during the trial.

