## 8. Efficacy assessment

Each day of the study following things will be performed:

a) study drug (glutamine or placebo) will be given intravenously during 12 h.

b) volume of infused solution and time interval of infusion will be registered.

c) total amount of nutrition during 24 h will be recorded.

d) SOFA score will be calculated.

End of ICU-stay will be recorded and as well as the route of discharge. If the patient is moved to another intensive care unit, the patient leaves the study. Still if the patient is treated more than 3 days, he is included and evaluated in the study although the ICU-stay is prolonged in another unit and patient during that time does not receive any controlled treatment. Provision of nutrition after ICU-stay (or after readmission to ICU) will not be recorded. If patient is readmitted to ICU within 24 h study protocol is continued. If patient is readmitted to ICU after more than 24 h the patient will not be included. Patient will not be included again in the study and the second (or consecutive) stay will not be recorded as ICU-stay in the protocol.

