# 19:3 Dosage of Dipeptiven or placebo

Body weight (kg)	Total dose (g/day)	Infusion rate (ml/h)
40	16.9	7.0
50	21.2	8.8
60	25.4	10.6
70	29.6	12.3
80	33.9	14.1
90 or more	38.1	15.9

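### Section 7's infusion rate of 0.183 mL/kg/h and the dosage table it cites (19:3) differ by about 4% at every listed weight, so they cannot both deliver 0.285 g glutamine/kg

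*Protocol*

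**What the plan says.** Section 7 (Treatment) sets a dose of 0.285 g glutamine per kg, infused over 12 h each day. It gives the product's content twice: as a solution "containing glutamine 0.13 g/ml", and again where the rate is derived. There it starts from the dipeptide, "As Dipeptiven contains 20 g alanyl-glutamine per 100 mL", and continues "corresponding to 13 g of glutamine per 100 mL, the infusion rate will be 0.183 mL/kg body weight/h". Weight-based dosing stops at an upper limit: "The dosage of glutamine in relation to body weight will not continue above 90 kg".

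Straight after the rate, section 7 refers to Appendix 8.4. The appendices have since been renumbered. The protocol's other old-style references are 8:2 for the SOFA table, 8.3 for Harris-Benedict and 8.5 for the report form, so 8.4 is the dosage table, now 19:3.

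Table 19:3 covers Dipeptiven and placebo together. For 40, 50, 60, 70, 80 and 90 kg or more it lists total doses of 16.9, 21.2, 25.4, 29.6, 33.9 and 38.1 g/day, and rates of 7.0, 8.8, 10.6, 12.3, 14.1 and 15.9 mL/h. It does not say whether the grams are glutamine or alanyl-glutamine.

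Delivery is recorded daily. Section 8 states that "volume of infused solution and time interval of infusion will be registered", and section 5:2 likewise that the amount given and the "time interval of administration will be registered and reported daily".

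**The concern.** Section 7 presents the per-kg rate and the table as two forms of one instruction. If they give different rates, a unit that sets the pump from the table and a unit that multiplies weight by 0.183 will give different doses under the same protocol, and only one of them can be giving 0.285 g/kg. The trial is planned for 20 to 25 centres, so both practices could well occur. The glutamine dose that the trial reports is also affected, because recorded millilitres can be turned into grams only with a concentration, and the two places imply different ones.

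**Working it through.** **Inputs.** Dose 0.285 g glutamine/kg, duration 12 h, glutamine content 0.13 g/mL, dipeptide content 0.20 g/mL and cap 90 kg (all section 7); doses and rates by weight (table 19:3).

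**1. Section 7's own figure.** 0.285 / 12 = 0.02375 g/kg/h, and 0.02375 / 0.13 = 0.1827, printed as 0.183 mL/kg/h. The figure is reproduced.

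**2. Section 7 against the table.**

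| Weight (kg) | 0.183 × weight (mL/h) | Table 19:3 (mL/h) | Table relative to section 7 | Table rate per kg |
|---|---|---|---|---|
| 40 | 7.32 | 7.0 | -4.4% | 0.175 |
| 50 | 9.15 | 8.8 | -3.8% | 0.176 |
| 60 | 10.98 | 10.6 | -3.5% | 0.177 |
| 70 | 12.81 | 12.3 | -4.0% | 0.176 |
| 80 | 14.64 | 14.1 | -3.7% | 0.176 |
| 90 | 16.47 | 15.9 | -3.5% | 0.177 |

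Rounding to 0.1 mL/h can account for at most 0.05 / 7.0 = 0.7%, and it would not always act in the same direction.

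**3. Is the table sound in itself?** If its grams are dipeptide, the rate is grams / (12 × 0.20). This gives 7.04, 8.83, 10.58, 12.33, 14.13 and 15.88 mL/h, which round to the six printed rates. If the grams were glutamine at 0.13 g/mL, the 40 kg row would need 16.9 / (12 × 0.13) = 10.8 mL/h, not 7.0. The grams are therefore dipeptide, and six consistent pairs rule out a single misprint or a broken table.

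**4. What content does the table imply?** A single dose of 0.4232 to 0.4235 g dipeptide/kg reproduces all six gram entries. If it is to supply 0.285 g glutamine/kg, the content is 20 × 0.285 / 0.4235 = 13.46 to 20 × 0.285 / 0.4232 = 13.47 g per 100 mL.

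**5. Dose delivered under each content.**

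- Content 13.46 g per 100 mL: section 7 delivers 0.183 × 12 × 0.1346 = 0.296 g/kg (+3.7%). The table, by rate × 12 × 0.1346 / weight, delivers 0.283 to 0.285 g/kg.
- Content 13.0 g per 100 mL: section 7 delivers 0.183 × 12 × 0.13 = 0.285 g/kg. The table delivers 0.273 to 0.276 g/kg (3.3% to 4.2% short).

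**6. Size per day.** At 70 kg: 12.81 × 12 = 153.7 mL against 12.3 × 12 = 147.6 mL, a difference of 6.1 mL or about 0.8 g glutamine. At the 90 kg cap: 197.6 against 190.8 mL, a difference of 6.8 mL or about 0.9 g.

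**The case against.** The strongest reply is that section 7 is not silent on what controls the dose. It tells the unit to calculate the volume from the 0.285 g/kg formula and cites the table as the tabulation of the result. That is fair. But the table does not tabulate that result, and nothing says what to do when they differ. The cross-reference makes the mismatch plainer rather than resolving it.

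It is also fair that the practical effect is slight. The difference is 0.3 to 0.6 mL/h, applies to drug and placebo alike, leaves blinding intact and concerns no endpoint. Delivered volume is on record. All of this stands.

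Four stronger readings are tempting, and the documents do not support them.

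- A reader might infer that section 7 is the place in error because 13 g is a rounded figure. The protocol never calls it rounded. The 13.46 is back-calculated on the assumption that the table is right.
- A reader might blame the rounding of 0.02375 to 0.024 in "corresponding to a infusion rate of 0.024 g/kg body weight/h". It plays no part: 0.024 / 0.13 would give 0.185, so the printed 0.183 came from the unrounded value.
- A reader might take the table's grams as glutamine and see a dose of 16.9 / 40 = 0.42 g/kg, far above 0.285. The printed rates fit only dipeptide.
- A reader might conclude that the table should simply govern. With 10 kg steps and no interpolation rule, that would cost more than it cures. At 45 kg, 0.176 mL/kg/h gives 7.92 mL/h, and the neighbouring rows are 12% below and 11% above it. At 85 kg (14.96 mL/h) they are 6% below and 6% above.

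**Conclusion.** The inconsistency is real and minor. Section 7's rate and table 19:3 differ by 3.5% to 4.4% in every row, always in the same direction, and one of them misses the stated dose by about 4%. This much rests only on figures printed in the protocol.

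Which of the two is wrong depends on the product's true glutamine content, which the protocol gives only to two figures. The table's internal consistency makes about 13.46 g per 100 mL, and hence a correction to section 7, the likelier outcome, but that needs confirmation.

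There is no effect on bias, power or the between-arm comparison. What is affected is uniformity of dose between units and the accuracy of the reported dose: converting recorded volumes at 13.0 when the content is 13.46 would understate glutamine by 1 - 13.0 / 13.46 = 3.4%.

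**What to change.** 1. Confirm the product's glutamine content to at least three figures.
2. If it is about 13.46 g per 100 mL, change section 7 to about 0.135 g/mL and 0.176 mL/kg/h (0.285 / 12 / 0.135 = 0.1759). If it is exactly 13.0, keep section 7 and recalculate both columns of table 19:3 at 0.183 mL/kg/h.
3. State that the corrected per-kg rate, capped at 90 kg, sets the pump and that table 19:3 is an illustration. At 0.176 the 90 kg row would read 15.8 (0.176 × 90 = 15.84) rather than 15.9 mL/h. The 0.1 mL/h has no dosing importance, but the precedence sentence settles it.
4. Label the table's total-dose column as grams of alanyl-glutamine, and update the reference from Appendix 8.4 to 19:3.
5. Compute the reported glutamine dose from the recorded volumes with the confirmed concentration.

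The cost is one product check, a few corrected figures and labels, one sentence on precedence and a notice to the units. No new data are needed.
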